#### 7.3 Randomisation

**For the main trial**, participants will be randomised in a 1:1 ratio to aspirin or aspirin + metformin, with minimisation by BCSP centre. The main trial is open-label, so the research team and participants will be aware of their treatment assignment. However, we will minimise potential bias at the surveillance colonoscopy, by asking participants and the research team not to reveal their treatment assignment to endoscopy staff.

**For the resveratrol sub-trial**, two doses of resveratrol (5mg and 1g) are compared against a placebo control group. Participants will be randomised equally in a 1:1:1 ratio to the three treatment arms and according to aspirin or metformin use, ensuring an even distribution across arms of these factors. The sub-trial will be double-blinded, so the research team and participants will not be aware of treatment assignment.

# 7.3.1 Method of implementing the randomisation/allocation sequence

The LCTU will supply a web-based randomisation system from a third party (Sealed Envelope Ltd.).

Once the participant has provided written informed consent to the trial and a physician has confirmed eligibility, randomisation will be performed. Site personnel (delegated and trained) will enter data pertaining to consent, eligibility, pseudonymised identification etc. onto the randomisation Case Report Form (CRF). These data are required to be input into the online randomisation system in order to allocate the participant to a treatment arm. The randomisation system will generate a unique trial ID and determine treatment consignment.

**For the main trial**, the research and pharmacy teams will be notified of which treatment the participant has been randomised to.

For the resveratrol sub-trial, the research and pharmacy teams will receive kit IDs for dispensing and will be blinded to the treatment allocation.

A copy of the confirmation email received following each randomisation will be printed out and filed in the Investigator Site File.

IRAS: 1005142 Page **48** of **109** 

Access to both Sealed Envelope randomisation systems is restricted and will be provided to the trial statistician for safety and DMC reporting, site research staff, pharmacy staff, LCTU trial management staff and Sponsor.

# 7.4 Blinding

The main trial will be open-label and will not contain a placebo. Accordingly, steps were taken at the funding stage to investigate and minimise potential bias. A survey of Endoscopists conducted by [name] (co-investigator) suggests bias at surveillance colonoscopy is unlikely to be an issue as the majority won't have any preconceptions around the benefits of each intervention, whilst the close monitoring, high standards and strict protocols in the BCSP means it is unlikely that Endoscopists will modify their behaviour because a patient is in a particular arm of the trial. The BCSP is a quality assured system in which the ADR of each Endoscopist is closely monitored and withdrawal times for each procedure are recorded. To diminish potential bias at the surveillance colonoscopy, we will blind Endoscopy staff (outcome assessors) and will instruct the participants and research staff not to divulge what arm an individual patient has been randomised to. Furthermore, the DMC will regularly review the colonoscopy withdrawal times across treatment groups, which would flag up a potential change in Endoscopist behaviour. Lab staff will be blinded to the treatment allocation during all their analyses.

The resveratrol sub-trial will be blinded. Participants, investigators, and all involved in trial conduct, sample analysis, outcome assessors, sponsor, or with any other interest in this trial will remain blind to the randomised treatment assignments until after final analysis is complete. The exception to this is as follows;

The trial statistician will have access to the web-based randomisation database
of all randomised participants in order to prepare the unblinded DMC to make
safety decisions and complete end of trial analyses. The trial statistician will
receive the sequence and decode treatment allocations from the manufacturer
for inclusion into the web-based randomisation system.

The capsules for the sub-trial will be manufactured to contain doses of 5mg and 250mg resveratrol, with matched placebo. Both of the active doses of resveratrol and the placebo will be filled into the same sized capsule and weight-matched. Each participant will receive the same number of capsules, regardless of which arm they are randomised to. All capsules will be matched to maintain blinding.

The sequence and decode of treatment allocations will remain concealed until after the creation of a locked analysis data set.

A DMC will review the trial data periodically to assess patient safety and will have access to unblinded data as outlined and agreed in the DMC Charter. Data presented at the DMC will be prepared by the trial statistician and take the format of an open blinded session followed by a closed unblinded session (as appropriate) to prevent unblinding of the CI, trial manager and the rest of the trial team.

IRAS: 1005142 Page **49** of **109** 

# 7.5 Emergency Unblinding

Unblinding is only relevant for the resveratrol sub-trial.

Unblinding should generally only be considered in the event of a medical emergency (for example, an emergency operation is required or an overdose has been taken) where knowledge of the participant's treatment allocation would change clinical management. The scenario for this to happen for resveratrol is expected to be very unlikely. Wherever possible, unblinding should be avoided to protect the integrity of the COLO-PREVENT trial.

Unblinding can only be performed by the Investigator, an authorised delegate, the site pharmacy team or Sponsor via an access controlled system available through the web based Sealed Envelope System (https://www.sealedenvelope.com/access/).

If unblinding occurs, the Investigator must record the reason for unblinding, as well as the date and time of the event in the site file and medical notes. Corresponding information will be recorded in the CRF by the Investigator. It will also be documented at the end of the trial in any final trial report and/or statistical report. The site team will notify the Leicester Clinical Trials Unit and the Sponsor in writing as soon as possible following the code break, detailing the necessity of the code break. In the case of unblinding an individual participant for safety reasons, appropriate follow-up of safety related events is required until the event(s) has satisfactorily resolved. The written information will be disseminated to the Data Safety Monitoring Committee for review in accordance with the DMC Charter. SUSARs are required to be reported unblinded.

Unblinding of all participants will be undertaken by the trial statistician after the last participant has completed their final visit, and the database has been locked for the signal-seeking sub-trial.

#### 7.6 Baseline data

Baseline measures will be completed following obtaining of written informed consent, and prior to first dosing (see section 8.6). Please see Trial Assessments (section 7.7) below for assessment details.

#### 7.7 Trial assessments

The trial visit schedule and assessments are summarised in Tables 1 (main trial) and 2 (sub-trial). Trial assessments (e.g. FFQ) may be completed remotely by telephone consultation, where possible, and when necessary.

Randomisation occurs at visit 1 (T=0). Study drug will be started as close to randomisation as possible and following collection of the baseline faecal sample. Site staff will make telephone calls for visits 2 and 3 as close to the scheduled time points as possible, however a window of ±1 week is accepted. The exception is for participants randomised to the metformin arm on the main trial, where a window of +1 week will apply (in order to allow for the 4 week run-in period for dosing). All 6 monthly research visits and the exit surveillance colonoscopy (main trial: visits 4-8; resveratrol sub-trial: visit 4) visit have a window of ±2 weeks. For the final visit, which is in line with a routine consultation following the exit surveillance colonoscopy, a +1 week window applies to allow a sufficient period post last dose for collection of adverse events. Visit schedules are in relation to T=0 date.

IRAS: 1005142 Page **50** of **109** 

Each participant's actual visit schedule should be determined taking into account practical considerations, the allowed visit window and ensuring the participant has sufficient drug.

Details of all trial visits are presented below.

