#### 3.7 Table of endpoints/outcomes

Objectives	Outcome Measures	Timepoint(s) of evaluation of this outcome measure (if applicable)
Primary Objectives	Primary outcome	Exit surveillance colonoscopy
1) To assess the benefits and	Polyp number measured by	154 weeks for main trial
harms of combining metformin and aspirin	MPP (mean number of polyps per participant)	52 weeks for sub-trial
compared to aspirin alone for the prevention of colorectal	Secondary outcomes	Exit surveillance colonoscopy
polyps in patients with high risk finding identified through the BCSP.	Polyp Detection Rate (PDR, proportion of individuals with one or more qualifying* premalignant polyp(s) at surveillance)	
2) To assess whether Resveratrol prevents colorectal polyps in high risk individuals and identify the most active dose.	Advanced polyps (measured as MPP and PDR); these are defined as serrated polyp ≥10mm, serrated polyp with any dysplasia, adenoma ≥10mm, adenoma with high-grade dysplasia	Exit surveillance colonoscopy
	* Please refer to definition in figure 2	
	Polyp subtype based on histopathology (adenoma/serrated); also reported as MPP and PDR	Exit surveillance colonoscopy
	Location of polyps (right colon - any part of the colon proximal	Exit surveillance colonoscopy

IRAS: 1005142 Page **37** of **109** 

	T	
	to the splenic flexure; left colon  – the rectum and the colon distal to and including the splenic flexure)	
	Polyp size (maximum dimension in mm as described in the histopathology report or endoscopic size if no histopathological size available)	Exit surveillance colonoscopy
Secondary Objectives Safety	Adverse events, including clinically significant bleeding episodes and GI tolerability.	From first administration of IMP until the final visit at 156 weeks for the main trial and 52 weeks for the sub-trial
Compliance	Assessment of compliance (counting residual number of tablets/capsules).	Main trial: weeks 25, 52, 78, 104, 130 and 154
		Sub-trial: weeks 25 and 52
Exploratory Objectives	Measurement of molecular (glucose, insulin (HOMA), HbA1c, triglycerides, cholesterol, IGFBP-3, free IGF-1) and physical (BMI, waist circumference) markers of metabolic status.	Main trial: weeks 0, 25, 52, 78, 104 and 154  Sub-trial: weeks 0, 25 and 52
	Assessment of dietary patterns and fat intake using the EPIC FFQ.	Main trial: weeks 0, 52, 104 and 154
		Sub-trial: weeks 0 and 52

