# 7. TRIAL PROCEDURES

See Tables 1 and 2 for detailed visit structure and trial procedures.

IRAS: 1005142 Page **42** of **109** 

Table 1: Trial Assessments for Main Trial (Aspirin or Aspirin + Metformin; 3 year intervention; open-label)

Procedure (Time (T) in weeks)	Pre-trial BCSP colonoscopy	Research visit	Telephone call	Telephone call	Research visit	Research visit	Every 6 months Research visits	Exit surveillance colonoscopy	Post- surveillance colonoscopy telephone visit
		Visit 1 T= 0 weeks	Visit 2 T= 4 weeks	Visit 3 T= 12 weeks	Visit 4 T= 25 weeks	Visit 5 T= 52 weeks	Visits 6, 7 & 8 6 monthly	Visit 9 T= 154 weeks	Visit 10 T= 156 weeks
Colonoscopy (routine clinical procedure)	•	1 = 0 WOOKS	1= 4 WOOKS	1= 12 WCCKC	1 = 20 WCCRO	1 = 02 WCCKC	o monuny	•	1= 100 WCCKC
Provide trial information (PIS)	•								
Colonoscopy results (routine care)	•								•
Eligibility assessment		•							
Informed consent		•							
Medical History and Demographics		•							
Fasting blood samples & processing -safety & research b		•			•	•	• (visits 6 & 7 only)	•	
Blood serum pregnancy test if applicable		•						•	
Food Frequency Questionnaire (FFQ)		•				•	• (visit 7 only)	•	
BP measurement		•							
Concomitant medication recording		•	•	•	•	•	•	•	•
Eligibility confirmation & Randomisation		•							
Trial drug dispensing		ea	Increase metformin dose from 500mg OD to BD		•	•	•		
Research faecal sample		•				•		
 
(prior to colonoscopy)
 
	
Adverse Events		•c	•	•	•	•	•	•	•
Compliance (pill counting)					•	•	•	•	
Rectal biopsies								•	
Diagnostic FFPE blocks		•						•	
Last dose of trial drug								•	
End of trial participation									•

<sup>a Trial medication to start following collection of a baseline research faecal sample (obtained on a FIT kit). b Locally processed: fasting lipid profile, FBC, LFT, U&E, eGFR, HbA1c, glucose; annual vit B12 testing for metformin arm participants. Research samples: IGFBP-3, IGF-I, insulin, PK/PD, exploratory research biomarkers. c AEs recorded from first dose. Visits 2 & 3 have a ±1 week window, except for metformin arm participants where visit 2 has a window of +1 week. Visits 4-9 have a ±2 week window. Visit 10 has a +1 week window.

IRAS: 1005142

Table 2: Trial Assessments for Signal-Seeking Sub-Trial (Blinded allocation: resveratrol 5mg or 1g, or placebo; 1 year intervention)

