Procedure (Time (T) in weeks)	Pre-trial BCSP colonoscopy	Research visit	Telephone call	Telephone call	Research visit	Surveillance (research)	Post-surveillance colonoscopy
(Time (T) in weeke)	(1)					colonoscopy	telephone call
	-						
		Visit 1	Visit 2	Visit 3	Visit 4	Visit 5	Visit 6
		T= 0 weeks	T= 4 weeks	T= 12 weeks	T= 25 weeks	T= 52 weeks	T= 54 weeks
Colonoscopya	•					•	
Provide trial information (PIS)	•						
Colonoscopy results	● f						•
Eligibility assessment		•					
Informed consent		•					
Medical History and Demographics		•					
Fasting blood samples & processing						_	
-safety & research c		•			•	•	
Blood serum pregnancy test if applicable		•				•	
Food Frequency Questionnaire (FFQ)		•				•	
Concomitant medication recording		•	•	•	•	•	•
Eligibility confirmation & Randomisation		•					
Trial drug dispensing		•b			•		
Provision of urine sample d		•			•	•	
Research faecal sample		•				• (prior to colonoscopy)	
Adverse Events		● e	•	•	•	•	•
Compliance (pill counting)					•	•	
Rectal biopsies						•	
Diagnostic FFPE blocks		•				•	
Last dose of trial drug						•	
End of trial participation							•

<sup>a First colonoscopy is a routine clinical procedure, second colonoscopy is a research procedure. b Patient to commence their trial medication following collection of a baseline research faecal sample (obtained on a FIT kit). cLocally processed: FBC, LFT, U&E, eGFR, HbA1c, fasting lipid profile, glucose. Research samples: insulin, IGFBP-3, IGF-I, PK/PD, exploratory research biomarkers. d Urine will be collected from 20% of patients from randomly selected sites that are willing and able to collect urine. e Adverse events collected from first dose. f Where routine consultations are undertaken remotely following a screening colonoscopy, potential participants will need to be brought into hospital for visit 1.

Visits 2 & 3 have a ±1 week window. Visits 4 and 5 have a ±2 week window. Visit 6 has a +1 week window.

COLO-PREVENT Protocol 11/12/2024: Version 4.0

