## Sub-trial

All Adverse Events will be collected from first dose up to visit 6 (54 weeks), and recorded in the AE section of the eCRF.

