## 10.2 Recording and reporting SAEs, SARs AND SUSARs

All SAEs, except those defined as exempt above, and SUSARs occurring from first administration of trial drug up to the routine visit post-surveillance colonoscopy (visit 10 for the main trial; and visit 6 for the resveratrol sub-trial) or 14 days post cessation of trial treatment where this occurs earlier than protocolised, are subject to expedited reporting. This should be conducted in accordance with the Sponsor SOP for reporting SAEs and on the COLO-PREVENT SAE Report Form. Completed forms should be emailed to the Sponsor ([contact]) and Leicester CTU ([contact]) immediately and within 24 hours of the research staff becoming aware of the event. All SAEs will be reviewed and tracked by the Sponsor (or their delegate) until resolution. Monthly line listings of all SAEs are reviewed by the Director of Research and Development on a monthly basis. Please note: the 14 day safety monitoring period following last dose is greater than 5X half-lives of all trial drugs.

For each **SAEs / SUSARs** the following information will be collected:

- full details in medical terms and case description
- event duration (start and end dates, if applicable)
- action taken
- outcome
- seriousness criteria
- causality (i.e. relatedness to trial drug / investigation), in the opinion of the investigator
- whether the event would be considered expected or unexpected.

Any change of condition or other follow up information should be emailed to Sponsor and Leicester CTU as soon as it is available or at least within 24 hours of the information becoming available. Events will be followed up until the event has resolved or a final outcome has been reached.

IRAS: 1005142 Page **73** of **109** 

The causality and expectedness of the SAE should be assessed by the Investigator(s) or another delegated medic on the SAE form.

For participants on the main trial, section 4.8 of the SmPC for aspirin and metformin will be used to assess expectedness of events (known as the reference safety information).

For participants on the resveratrol sub-trial, section 8.0 of the IB for resveratrol will be used to assess expectedness of events (known as the reference safety information).

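### Timing every visit from T=0 lets a compliant final safety call fall 0 to 13 days after last dose, short of the stated 14 days, and section 3.7 ends sub-trial adverse events at week 52 rather than 54

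*Protocol*

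**What the plan says.** Section 7.7 sets the anchor for all visits: "Visit schedules are in relation to T=0 date". The footnote to Table 1 gives the main-trial windows: "Visits 4-9 have a ±2 week window. Visit 10 has a +1 week window". The footnote to Table 2 gives the sub-trial windows: "Visits 4 and 5 have a ±2 week window. Visit 6 has a +1 week window". Visit 9 (week 154) and visit 5 (week 52) are the exit colonoscopies. Visit 10 (week 156) and visit 6 (week 54) are the closing telephone calls.

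Sections 8.6 and 9.6 have participants stop trial drug on the day of the exit colonoscopy, so the colonoscopy date is the last-dose date.

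Section 7.7 gives the reason for the final-visit window: "a +1 week window applies to allow a sufficient period post last dose for collection of adverse events". Section 10.2 relies on a fixed post-dose period, noting that "the 14 day safety monitoring period following last dose is greater than 5X half-lives of all trial drugs". The trial summary describes follow-up as ending about 2 weeks after the exit colonoscopy, which is a different anchor from T=0.

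On the sub-trial's adverse-event period, the endpoint table in section 3.7 reads "From first administration of IMP until the final visit at 156 weeks for the main trial and 52 weeks for the sub-trial". Section 10.1.1 says for the sub-trial: "All Adverse Events will be collected from first dose up to visit 6 (54 weeks". Table 2 also records adverse events at visit 6, week 54.

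**The concern.** A post-dose safety period has to be counted from the last dose. Here the call that closes the period is counted from randomisation, while the last dose may shift by two weeks. The one-week allowance on the call cannot absorb a two-week delay in the colonoscopy. The calendar therefore does not secure the 14 days that section 10.2 treats as given.

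Harms belong to the first primary objective (section 3.1), and clinically significant bleeding is a named safety outcome (section 3.5). The exposed days follow a colonoscopy which, in the sub-trial, is a research procedure. Optional rectal biopsies may be taken at it, and section 2.4 acknowledges a rare risk of perforation or serious bleeding from them. Trial participation ends at the final call and no later contact is scheduled, so an event that surfaces afterwards may not be recorded.

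The week-52 entry in section 3.7 is a separate conflict. It sits in the table that defines the safety outcome and, read literally, it stops sub-trial adverse-event collection on the last-dose day.

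**Working it through.** **Inputs**
- Colonoscopy and last dose, C: week 154 ±2, so 152 to 156 (main trial); week 52 ±2, so 50 to 54 (sub-trial). Tables 1 and 2; sections 8.6 and 9.6.
- Final call, F: week 156 to 157 (main trial); week 54 to 55 (sub-trial). Tables 1 and 2.
- Anchor for both: T=0. Section 7.7.
- Stated post-dose period: 14 days. Section 10.2.

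**Step 1: the plan's own figure.** The gap in days is 7 × (F − C). At nominal dates it is 7 × (156 − 154) = 14 days, and 7 × (54 − 52) = 14 days. The stated 14 days is reproduced, but only at nominal timing.

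**Step 2: range within the allowed windows (main trial).**
- Shortest: 7 × (156 − 156) = 0 days. With the call a full week late: 7 × (157 − 156) = 7 days.
- Longest: 7 × (157 − 152) = 35 days.

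The sub-trial gives the same figures, since both its visits are 102 weeks earlier.

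**Step 3: when it falls short.** The gap is under 14 days when C > F − 2. With the call on its nominal date this means a colonoscopy after week 154 (sub-trial 52). With the call a week late it means a colonoscopy after week 155 (sub-trial 53).

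**Step 4: share of participants.** The protocol gives no distribution of colonoscopy dates, so one must be assumed. For a uniform date over the 4-week window, the share under 14 days is (156 − (F − 2)) / 4:

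| Final call | Share under 14 days |
|---|---|
| Nominal date (F = 156) | 2 / 4 = 50% |
| Mid-window (F = 156.5) | 1.5 / 4 = 37.5% |
| Full +1 week (F = 157) | 1 / 4 = 25% |

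Counting whole days (29 possible colonoscopy days), the extremes are 14/29 = 48% and 7/29 = 24%.

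**Step 5: sensitivity to the assumption.** With the call on its nominal date and skewed timing (beta distributions over the window), the share is about 11% to 31% if colonoscopies run early and 69% to 89% if they run late. With no timing assumption it can be anything from 0 to 100%.

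**Step 6: days lost.** Under uniform timing with the call on its nominal date, the gap is uniform over 0 to 28 days. The mean shortfall across all participants is 14² / (2 × 28) = 3.5 days. That is 3.5 / 1,092 = 0.3% of 156 weeks, or 3.5 / 378 = 0.9% of 54 weeks.

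**Step 7: section 3.7 against section 10.1.1.** At nominal timing, week 52 leaves 7 × (52 − 52) = 0 days after last dose in the sub-trial. Week 54 leaves 14.

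**Step 8: after re-anchoring.** With the call at 14 days after the actual last dose, +1 week, the gap is 14 to 21 days for everyone and the share under 14 days is 0%.

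**The case against.** The strongest reply is that the intention is plain. Section 7.7 describes the final visit as following the exit colonoscopy and gives its window expressly to allow time after last dose. The trial summary ties follow-up to the colonoscopy, and the visit tables define the contact as a post-colonoscopy call at which results are given. A call on the day of the colonoscopy fits none of these descriptions. Section 10.8 records adverse reactions for up to 14 days after last dose without reference to any visit, and section 14.11 allows later follow-up of an adverse reaction or unresolved serious event. The week-52 entry in section 3.7 is worded as the final visit, so it is probably a slip for week 54.

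Much of this stands, and it narrows the point. It does not remove it. The stated intention conflicts with the stated anchor, and a site applying the anchor literally would be compliant. The protection in section 10.8 covers adverse reactions only. All-cause adverse events and serious adverse events run to the final visit, and no later contact is scheduled at which a new event would come to light.

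Three stronger readings are tempting, and the documents do not support them.
- *Up to half of participants fall short.* Half is not a bound. It depends on symmetric colonoscopy timing and on every call being made on its nominal date.
- *The shortfall biases the comparison.* The visit schedule is the same in every arm, and what is lost is the later part of the 14 days.
- *Early stoppers are observed for less time in the adverse-event tables.* Section 10.2 closes expedited reporting of serious events at "14 days post cessation of trial treatment where this occurs earlier than protocolised". That governs the expedited route. Section 10.1.1 continues adverse-event recording to the final visit without a cut-off for early stoppers, section 7.10 asks them to keep attending, and section 10.4 records deaths to the final visit. A shorter window for expedited reporting than for recording is not in itself a contradiction.

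**Conclusion.** Two defects in the text hold. First, with visits timed from T=0, the protocol's own windows allow the final safety call 0 to 13 days after last dose, against the 14 days in section 10.2 and the roughly 2 weeks in the trial summary. This follows from the calendar alone and needs no assumption. Its frequency does need one: about 25% to 50% of participants under uniform colonoscopy dates, fewer if colonoscopies run early and more if they run late. The average loss is a few days, common to all arms. The consequence is incomplete capture of all-cause adverse and serious adverse events late in the post-dose period, not a distorted treatment comparison. Second, sections 3.7 and 10.1.1 disagree on whether sub-trial adverse-event collection ends at week 52 or week 54. Both are worth correcting because an analysis plan cannot recover events that were never collected.

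**What to change.** - In section 7.7 and Tables 1 and 2, time visit 10 (main trial) and visit 6 (sub-trial) from the actual exit colonoscopy/last-dose date, at 14 days with a +1 week window. All other visits can stay anchored on T=0.
- Reconcile section 3.7 with section 10.1.1 and Table 2 on the sub-trial's final visit (visit 6, week 54).
- Check that the week numbers given for the final visit in sections 3.7 and 10.1.1 read as nominal once the call follows the colonoscopy.

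The cost is wording in a few places and one date rule in the visit calendar. No visit is added, and calls move by at most about two weeks from their present nominal date.

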### **III. TRIAL SUMMARY**

Trial Title	COLO-PREVENT – A phase 2/3 randomised platform trial assessing the efficacy of aspirin, aspirin plus metformin, or resveratrol, for colorectal polyp prevention in patients undergoing surveillance in the national Bowel Cancer Screening Programme	
Short title	COLO-PREVENT: A platform for developing COLOrectal cancer PREVENTion therapies	
Trial acronym	COLO-PREVENT	
Chief Investigator	[name]	
Lead Applicant	[name]	
Joint Lead Applicant	[name]	
Clinical Phase	Main trial: Phase III Signal-Seeking sub-trial: Phase II	
Trial Design	Main trial: Interventional, preventative, multi-centre, open-label, parallel, randomised control trial.  Signal seeking sub-trial: Interventional, preventative multi-centre, double-blinded, pharmacodynamic, pharmacokinetic, mechanistic, placebo, parallel, randomised controlled trial.	
Trial Participants	Patients identified as high risk for colorectal cancer according to Bowel Cancer Screening Programme (BCSP) criteria. This includes: - patients with 'high risk' findings after completion of a BCSP screening episode - patients with a large non-pedunculated colorectal polyp	
Planned Sample Size	Main trial: 862 Sub-trial: 477 Total sample size for the two arms: 1339	
Treatment duration	Main Trial: 3 years Sub-Trial: 1 year	
Follow up duration	Participants are followed up until approximately 2 weeks after their exit surveillance colonoscopy	
Planned Trial Period	97 months (from FPFV to LPLV)	
Investigational Medicinal Product(s)	Aspirin Metformin Resveratrol	
Formulation, Dose, Route of Administration	Aspirin - 75mg tablets (enteric coated) to be taken orally once daily Metformin – 500 mg tablets to be taken orally twice a day with breakfast and evening meal Resveratrol – participants in the sub-trial will be randomised to receive one of the following blinded treatments to be taken once daily:  5mg resveratrol (1X 5mg resveratrol and 3X placebo tablets) 1g resveratrol (4X 250mg resveratrol)	

IRAS: 1005142 Page **15** of **109** 

	Placebo (4X placebo tablets)	

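### The final safety call is timed from randomisation, so an in-window but late exit colonoscopy can leave less than the stated 14 days of follow-up after last dose

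*Protocol*

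**What the plan says.** Section 7.7 of the protocol anchors every visit to randomisation: "Visit schedules are in relation to T=0 date". For the final visit it adds that "a +1 week window applies to allow a sufficient period post last dose for collection of adverse events".

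The windows are in the table footnotes of section 7. For the main trial (Table 1): "Visits 4-9 have a ±2 week window. Visit 10 has a +1 week window". For the sub-trial (Table 2): "Visits 4 and 5 have a ±2 week window. Visit 6 has a +1 week window". Visit 9 is the main-trial exit colonoscopy at week 154 and visit 10 the closing telephone call at week 156. In the sub-trial, visit 5 is the research colonoscopy at week 52 and visit 6 the closing call at week 54.

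Sections 8.6 and 9.6 have the participant stop trial drug on the day of that colonoscopy. Section 10.1.1 ends adverse-event collection at visit 10 and visit 6, and section 10.2 ends routine SAE reporting at the same visits.

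Three places describe follow-up in relation to the last dose or the colonoscopy instead:

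- Section 10.2 asserts that "the 14 day safety monitoring period following last dose is greater than 5X half-lives of all trial drugs".
- Section 10.8 has adverse reactions recorded for up to 14 days after the last dose, and SUSARs reported however late they occur.
- The Trial Summary says: "Participants are followed up until approximately 2 weeks after their exit surveillance colonoscopy".

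The safety row of the section 3.7 table gives the collection period as "From first administration of IMP until the final visit at 156 weeks for the main trial and 52 weeks for the sub-trial".

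**The concern.** One set of passages counts follow-up from the last dose or the colonoscopy; the operative schedule counts it from randomisation. The two agree only if the colonoscopy is on its nominal date. The colonoscopy may move by two weeks either way, while the final call may only be up to one week late and has no link to when the colonoscopy took place. A site can therefore keep to every visit window and still close adverse-event collection less than 14 days after the last dose.

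The days concerned matter for safety. Clinically significant bleeding is a named safety outcome (section 3.5). Up to six optional research biopsies are taken at this colonoscopy, and section 2.4 itself mentions a rare, theoretical risk of perforation or serious bleeding from them. In the sub-trial the colonoscopy is itself a research procedure. Length of follow-up after it would vary between participants for scheduling reasons alone.

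**Working it through.** **Inputs.** Anchor T=0 (section 7.7). Nominal colonoscopy weeks 154 and 52; nominal final-call weeks 156 and 54 (section 7.7 visit lists). Colonoscopy window ±2 weeks, so weeks 152–156 and 50–54; final-call window +1 week, so weeks 156–157 and 54–55 (Table 1 and 2 footnotes). Last dose on the day of colonoscopy (sections 8.6 and 9.6).

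**Reproducing the stated figure.** At nominal dates the gap is 7 × (156 − 154) = 14 days in the main trial and 7 × (54 − 52) = 14 days in the sub-trial. The 14 days of section 10.2 is recovered.

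**General formula.** Let d be the number of days by which the colonoscopy departs from its nominal date, from −14 to +14 (29 permitted days). The earliest permitted call then comes 14 − d days after the last dose and the latest 21 − d days after it. Both trials give the same values:

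| Colonoscopy | Main / sub-trial week | Days to final call (earliest–latest) |
|---|---|---|
| 2 weeks early | 152 / 50 | 28–35 |
| 1 week early | 153 / 51 | 21–28 |
| On time | 154 / 52 | 14–21 |
| 1 week late | 155 / 53 | 7–14 |
| 8 days late | 155 + 1 day / 53 + 1 day | 6–13 |
| 2 weeks late | 156 / 54 | 0–7 |

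**How much of the window is affected.**

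- 14 − d ≥ 14 requires d ≤ 0: 15 of 29 days, where 14 days is guaranteed.
- For d from +1 to +7 (7 of 29 days), 14 days is reached only if the call uses part or all of its extra week.
- 21 − d < 14 requires d ≥ 8: for d from +8 to +14 (7 of 29 days), no in-window call reaches 14 days.

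So on 7 + 7 = 14 of the 29 permitted days a fully compliant call can give less than 14 days.

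**Is there a backstop?** Section 10.2 has a 14-day rule for SAEs, but it is for participants who stop treatment before the planned time. A participant who completes treatment and has a late, in-window colonoscopy is not covered by it, and may have a shorter SAE reporting period than one who stopped early. Visit 10 and visit 6 are the end of trial participation and no later contact is scheduled.

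**With the call timed from the colonoscopy.** A call at 14 days with a +1 week window gives 14–21 days for every d. At d = +14 it falls at week 156 + 2 = 158, up to 159 (sub-trial 56–57). At d = −14 it falls at week 152 + 2 = 154, up to 155 (sub-trial 52–53).

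**Section 3.7.** The safety row puts the sub-trial's final visit at 52 weeks. Section 7.7 and section 10.1.1 put it at visit 6, week 54. Week 52 is the colonoscopy visit.

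**The case against.** The best reply is that the intent is plain and much of the safety cover does not depend on the call date. Section 10.2 ends SAE reporting at the visit after the surveillance colonoscopy, giving visit numbers and no week. Section 10.8 records adverse reactions to 14 days after last dose whenever the call takes place, and sets no time limit for SUSARs. Section 10.1 defines a reaction broadly, as one where a link cannot be ruled out, so a bleed soon after the last aspirin dose could well qualify. Section 7.7 also lets each participant's schedule reflect practical considerations, though still within the allowed windows.

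Most of this stands, and it rules out several stronger readings that a reader might infer:

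- *Late colonoscopies generally get 0–7 days.* That range applies only on the last permitted day. A zero-day gap is also implausible, since the call is where colonoscopy results are given.
- *Delayed bleeds after colonoscopy go unrecorded.* Those judged related to the drug remain within section 10.8. What is exposed is actively collected adverse events and SAEs not judged drug-related, including purely procedural ones.
- *A colonoscopy after week 157 falls after collection has closed.* Collection runs to visit 10, which by definition follows the colonoscopy; so late a procedure would be a visit-window deviation.
- *The arms are compared unfairly.* Both arms of the main trial, and all three of the sub-trial, share one schedule. The shortfall is not arm-dependent by design.
- *Section 3.7 excludes everything after the sub-trial colonoscopy.* The cell also refers to the final visit, which is visit 6, so 52 weeks reads as a slip.

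What does not stand is that intent settles the matter. The T=0 sentence and the footnotes are what sites schedule from, and they conflict with the 14 days.

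**Conclusion.** The point holds as a minor but real inconsistency. Following the schedule exactly does not always deliver the 14-day period that section 10.2 relies on, or the two or so weeks in the Trial Summary. The shortfall is certain on 7 of 29 permitted colonoscopy days and possible on 7 more; on the other 15, follow-up is at least 14 days.

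These are shares of the window, not of participants: the documents do not say how many colonoscopies will be late. The result assumes that section 7.7 and the footnotes are applied literally and that the last dose is on the day of colonoscopy. It concerns participants who complete treatment. It does not touch the primary endpoint, and nothing in the documents shows bias between arms.

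**What to change.** In section 7.7, exempt the final visit from the T=0 rule. Time visit 10 (main trial) and visit 6 (sub-trial) from the actual colonoscopy and last-dose date, at the protocol's own 14 days with the existing +1 week window. Align the footnotes to Tables 1 and 2, the week numbers in section 10.1.1, and the wording of sections 10.2 and 10.8 and the Trial Summary, so that all describe the same period. In the section 3.7 safety row, replace the sub-trial's 52 weeks with the visit 6 timing.

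The cost is one sentence, two footnotes, one table cell and matching wording in the sections named. Some calls would move by up to two weeks: later after a late colonoscopy (to weeks 158–159, or 56–57 in the sub-trial) and earlier after an early one. After an early colonoscopy, follow-up comes down from as much as 28–35 days to 14–21, so that everyone who completes treatment has the same period.
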